6. STUDY PROCEDURES

Study visits

Visits	Procedures
Visit 1 – before surgery	
- Obtain informed consent- ADL questionnaire (see next section)- Visual analog scale for pain (VAS): pain on a scale of 1 to 10 
The measurements are part of standard care and performed by caregivers
 
- Perform the following measurements: range of motion of the PIP joint of the affected finger (including noting any flexion contracture), distance fingertip to distal palmar crease (DPC), and grip strength using Jamar 2 setting.
Visit/Telephone call 2 (2-4 days after surgery)	
- Take the following questionnaire:
1. Are you able to return to activities of daily living, and what activities do you still have trouble doing? You can list the activities you are having trouble with.2. VAS3. How many oxycodone or other narcotic medications are you taking post-op4. Are you able to return to work?

	
5. Are you satisfied with the procedure, and would you choose to have it again for a similar problem?
 
- Take the ADL questionnaire (see next section)- If in person (part of standard care, only collected by study staff, measurements performed by caregivers): Perform the following measurements: range of motion of the PIP joint of the affected finger (including noting any flexion contracture), distance fingertip to distal palmar crease (DPC), and grip strength using Jamar 2 setting.
Visit/Telephone call 3 (6-8 days after surgery)	
- Take the following questionnaire:
1. Are you able to return to activities of daily living, and what activities do you still have trouble doing? You can list the activities you are having trouble with.2. VAS3. How many oxycodone or other narcotic medications are you taking post-op4. Are you able to return to work?5. Are you satisfied with the procedure, and would you choose to have it again for a similar problem?- Take the ADL questionnaire (see next section)- If in person (part of standard care, only collected by study staff, measurements performed by caregivers): Perform the following measurements: range of motion of the PIP joint of the affected finger (including noting any flexion contracture), distance fingertip to distal palmar crease (DPC), and grip strength using Jamar 2 setting.

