Visit/Telephone call 4 (13-15 days after surgery)	
- Take the following questionnaire:
1. Are you able to return to activities of daily living, and what activities do you still have trouble doing? You can list the activities you are having trouble with.2. VAS3. How many oxycodone or other narcotic medications are you taking post-

	
op
 
4. Are you able to return to work?
 
5. Are you satisfied with the procedure, and would you choose to have it again for a similar problem?
 
- Take the ADL questionnaire (see next section)- If in person (part of standard care, only collected by study staff, measurements performed by caregivers): Perform the following measurements: range of motion of the PIP joint of the affected finger (including noting any flexion contracture), distance fingertip to distal palmar crease (DPC), and grip strength using Jamar 2 setting.-
Visit/Telephone call 5 (27-29 days after surgery)	
- Take the following questionnaire:
1. Are you able to return to activities of daily living, and what activities do you still have trouble doing? You can list the activities you are having trouble with.2. VAS3. How many oxycodone or other narcotic medications are you taking post-op4. Are you able to return to work?5. Are you satisfied with the procedure, and would you choose to have it again for a similar problem?- Take the ADL questionnaire (see next section)- If in person (part of standard care, only collected by study staff, measurements performed by caregivers): Perform the following measurements: range of motion of the PIP joint of the affected finger (including noting any flexion contracture), distance fingertip to distal palmar crease (DPC), and grip strength using Jamar 2 setting.-
Visit/Telephone call 6 (3 months +- 1 week after surgery)	
- Take the following questionnaire:
1. Are you able to return to activities of daily living, and what activities do you still have trouble doing? You can list the activities you are having trouble with.

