- Range of motion of the PIP joint of the affected finger using a goniometer (in degrees), including any flexion contracture + Distance of fingertip from DPC
- Grip strength in the affected as well as contralateral hand using a dynamometer at Jamar 3 setting (in lbs)
- Return to activities of daily living. One question is: 'What activities can't you do?'. We also take a questionnaire to rate their ability to do certain activities (see questionnaire under this section). Patients can rate their ability to perform each activity on a scale from 1 to 5 (1 indicating no difficulty and 5 indicating unable to perform).
- VAS (a pain scale from 1 – 10, reported by the patient)
- How many oxycodone or other narcotic medications are you taking post-op? The number of pills taken will be given.
- Return to work. Patients give a date of when they started working again. Then we'll calculate the return to work in weeks
- Are you satisfied with the procedure, and would you choose to have it again for a similar problem? Answered with yes or no.
- Complications (i.e., trigger finger recurrence, infection, bleeding, etc.)

ADL questionnaire

Mass General Brigham Institutional Review Board
Intervention/Interaction Detailed Protocol

Opening jar	1	2	3	4	5
Driving	1	2	3	4	5
Household Chores	1	2	3	4	5
Carrying Groceries	1	2	3	4	5
Buttoning	1	2	3	4	5
Bathing	1	2	3	4	5
Cooking	1	2	3	4	5
Writing	1	2	3	4	5
Dressing	1	2	3	4	5
Shopping	1	2	3	4	5
Holding a book	1	2	3	4	5
Eating	1	2	3	4	5
Using a Computer	1	2	3	4	5
Holding a Phone	1	2	3	4	5
Using Toilet	1	2	3	4	5

Description of plans for return of research results as applicable

Not applicable

Definition of primary and secondary outcomes/endpoints

Primary endpoints:

- The 5 questions asked in the section above, together with the *ADL questionnaire*
- Recurrence of trigger finger or incomplete release

Secondary endpoints:

- Range of motion of the PIP joint of the affected finger (including noting any flexion contracture)
- Distance fingertip to distal palmar crease
- Grip strength in the affected hand
- Other complications than recurrence of trigger finger or incomplete release

Local site restrictions or site-specific procedures as applicable

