We will use a student t-test to analyze normally distributed continuous data. When we compare data at two different time points within a group, we will use a paired student t-test. When we compare continuous data of two different groups, we will use an unpaired student t-test.

We will use a Mann-Whitney U test if the continuous data is not normally distributed.

We will use Fischer's exact test or a Chi-squared test for differences in categorical variables, depending on the number of events in the different groups.

Power analysis

We have performed a power analysis to find differences between two independent means (normally distributed) with alpha = 0.05, power = 0.80, and effect size 0.5. This would require a total sample size of 102 patients (51 in each group). If the data is non-normally distributed with the same alpha, power, and effect size, we would need a total of 106 patients (53 in each group).

This power analysis is performed for our most important primary outcomes: the 5-question and ADL questionnaires.

5. Monitoring and Quality Assurance

The full-time research coordinator and principal investigator are responsible for adherence to all IRB policies and guidelines and for the accuracy and completeness of all forms, entries, and informed consent.

Study data will be maintained in a locked filing cabinet and/or on password-protected computers. Questionnaires and self-reported responses will not become part of the subject's medical record. Hard copies of study-related data and forms will be stored in a lockable file cabinet. Only the investigators and study staff will have access to this information. Any magnetic or electronic information will be saved in password-protected computers, which only study staff members can access. REDCap, secure and HIPAA-compliant, will be used to collect all answers.

For guidance, refer to the following Partners policies:

Data and Safety Monitoring Plans and Quality Assurance

https://partnershealthcare-public.sharepoint.com/ClinicalResearch/DSMP_in_Human_Subjects_Research.pdf

Reporting Unanticipated Problems (including Adverse Events)

https://partnershealthcare-public.sharepoint.com/ClinicalResearch/Reporting_Unanticipated_Problems_including_Adverse_Events.pdf

6. Privacy and Confidentiality

- Study procedures will be conducted in a private setting
- Only data and/or specimens necessary for the conduct of the study will be collected

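### Primary question 5 asks about satisfaction and willingness to repeat under one yes/no answer, so a no cannot be attributed to either half

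*Combined protocol and SAP*

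**What the plan says.** The list of variables in section 6 (Specific data variables to be collected) gives the item and its response format together: "Are you satisfied with the procedure, and would you choose to have it again for a similar problem? Answered with yes or no".

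The visit table in the same section numbers it as a single question, "5. Are you satisfied with the procedure, and would you choose to have it again for a similar problem", and asks it at each of the six postoperative contacts (visits 2 to 7, from 2-4 days to 6 months). No second response field, no rule for a mixed answer and no follow-up reason for a no appears anywhere.

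The item has primary status. The first primary endpoint is "The 5 questions asked in the section above, together with the" ADL questionnaire, and the Power analysis paragraph under Statistical Analysis states: "This power analysis is performed for our most important primary outcomes: the 5-question and ADL questionnaires".

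**The concern.** Being satisfied with an operation and being willing to have it again are related but distinct outcomes. A patient who is content with the result but would not repeat the operation, or who is disappointed but would still repeat it, is given one box. Some will answer on the first half, some on the second, and some will say yes only if both hold. Contacts may be in person, by telephone or by e-mail link, so the way a mixed view is settled may also vary with how the question is put.

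The Benefits section says the results should support shared decision-making between patients and physicians. Satisfaction rates and the share who would have the procedure again are both natural figures for that purpose. As collected, the study can report neither.

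**Working it through.** **1. Can the halves be recovered from other data?** Question 1 also has two parts, but it invites the patient to list activities, so its second part has an outlet. Question 5 has none. The other variables are pain, narcotic use, return to work, the ADL ratings, the clinical measurements and complications. None of them records satisfaction or willingness separately. The loss is therefore permanent once the answer is entered.

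**2. What does an answer mean if read literally?** Let S be satisfied and W be willing to repeat. A yes means S and W. A no covers three states: S without W, W without S, or neither. The data do not distinguish them.

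**3. The plan's own figure.** There is no sample-size calculation for a yes/no outcome. The stated calculation is for two means with "alpha = 0.05, power = 0.80, and effect size 0.5", giving 51 per group, or 53 for non-normal data. A one-sided t-test gives n = 50.15, rounded up to 51 (power at 51 is 0.806). Dividing by the Mann-Whitney efficiency of 0.955 gives 50.15 / 0.955 = 52.5, rounded up to 53. Both stated figures are reproduced. The plan does not state sidedness; a two-sided t-test would need 64 per group. None of this depends on how question 5 is worded. It supplies only the 51 per arm used below.

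**4. What might the combination do to the comparison?** The documents give no rates, so every rate here is assumed. Take willingness of 95% in one arm and 80% in the other, 51 per arm, two-sided 5%. Power is the exact sum over all pairs (a, b) of Bin(a; 51, p1) × Bin(b; 51, p2), counting the pairs where the test gives p ≤ 0.05. For the combined item, p = P(S and W). This equals P(S) × P(W) if the answers are independent, P(W) × P(S given W) in general, and the smaller of P(S) and P(W) if they are fully nested.

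| Assumption about satisfaction | p1 vs p2 | Difference (points) | Fisher | Chi-squared |
|---|---|---|---|---|
| Willingness asked alone | 0.95 vs 0.80 | 15 | 52% | 66% |
| 90% in both arms, nested | min(0.90, 0.95) = 0.90 vs min(0.90, 0.80) = 0.80 | 10 | 20% | 29% |
| 90% in both arms, independent | 0.90 × 0.95 = 0.855 vs 0.90 × 0.80 = 0.72 | 13.5 | 31% | 39% |
| 98% of willing patients satisfied, both arms | 0.98 × 0.95 = 0.931 vs 0.98 × 0.80 = 0.784 | 14.7 | 46% | 58% |
| 95% vs 85%, independent | 0.95 × 0.95 = 0.9025 vs 0.85 × 0.80 = 0.68 | 22.25 | 75% | 81% |

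The combined item can weaken the contrast, leave it nearly unchanged, or strengthen it. In the last row satisfaction asked alone, 0.95 vs 0.85, has Fisher power of only 25% by the same sum. Splitting therefore does not always gain power.

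**The case against.** The strongest reply is that the item still works as a coarse composite. Read literally, it compares between arms the proportion who are both satisfied and would repeat, and Fisher's exact or the chi-squared test can be applied to it as the plan intends. This stands in part. It would be too strong to call a no uninterpretable: it means that at least one half failed. What is missing is which half, together with any assurance that patients with mixed views read the question literally.

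A reader might also infer that the combination dilutes a difference between techniques, because willingness to repeat is the half specific to technique. The documents do not support this. Both halves refer to the same object, the procedure the patient received, and neither asks about the other technique. Whether any dilution occurs depends on rates and a correlation that the plan does not give; under one plausible assumption in the table the combined item has more power than willingness alone.

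Finally, this is one binary item beside four other questions and a 15-item ADL form, and no study conclusion is shown to turn on it. That is fair, and it limits the weight of the point.

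**Conclusion.** The point holds as a flaw in how a primary item is measured. One answer serves two outcomes, no rule covers mixed answers, and the halves cannot be separated afterwards. This follows from the wording alone and needs no assumption.

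The size of the effect on the between-group comparison is unknown. The Fisher range of about 20% to 75%, against 52% for willingness alone, rests on assumed rates, assumed dependence between the answers, 51 per arm and a two-sided 5% test. It shows that the direction is not fixed; it does not estimate a loss. The case for change is that each answer can be attributed and reported, not that power will rise. Priority is low, but the change is cheap and the missing detail cannot be recovered later.

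**What to change.** At each postoperative contact, replace question 5 with two separate yes/no items:

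- *Are you satisfied with the procedure?*
- *Would you choose to have the same procedure again for a similar problem?*

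Name the satisfaction item, at one prespecified contact, as the component of the primary set. Report willingness to repeat descriptively, as frequencies and percentages by group, so that the split adds no confirmatory test. Amend the visit table, the variable list and the references to five questions in the endpoint and power paragraphs to match.

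If enrolment has begun, keep the combined answers already collected and report them separately; they cannot be recoded into either new item.

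The cost is one extra REDCap field and seconds per contact. The e-mail and telephone scripts do not contain the item and need no change. The trade-off is that satisfaction alone may separate the groups less well than the combined item if both outcomes favour the same technique, as in the last row of the table.

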Institutional Review Board Intervention/Interaction Detailed Protocol

Principal Investigator: [name]

Project Title: Clinical and Patient-Reported Outcomes After Ultrasound-guided vs. Open Trigger Finger Release

Version Date: 6/6/2023

For Intervention/Interaction studies, submit a Detailed Protocol that includes the following sections. If information in a particular section is not applicable, omit and include the other relevant information.

1. Background and Significance

Trigger finger is initially treated conservatively. Conservative treatment options include modification of activities, painkiller administration, splinting, and corticosteroid injections (1). Open or minimally invasive surgical treatment can be considered if conservative treatment fails. Minimally invasive surgery options consist of ultrasound-guided or blind percutaneous trigger finger release.

Many studies have reported good clinical outcomes after ultrasound-guided trigger finger release, including low rates of catching or locking recurrence rates, high QuickDASH scores and high patient satisfaction (2-4).

Postoperative clinical outcomes of open surgery have been widely compared to percutaneous surgery (5-8). However, the comparison of postoperative results between ultrasound-guided and open trigger finger release has been scarcely reported. Nikolaou et al. reported that ultrasound-guided trigger finger release resulted in a significantly sooner return to normal activities and better patient-reported cosmetic outcomes than open trigger finger release (9). Success rates and mean QuickDASH scores did not differ significantly between these groups in this cohort.

The potential benefits of ultrasound-guided trigger finger release compared to open trigger finger release have yet to be investigated. This study aims to prospectively analyze patient-reported outcomes in patients undergoing open vs. ultrasound-guided trigger finger release.

2. Specific Aims and Objectives

This study aims to prospectively analyze clinical and patient-reported outcomes in patients undergoing open vs. ultrasound-guided trigger finger release. Patients will not be randomly assigned to one of these two groups; rather, they will undergo the type of trigger finger surgery that they already agreed to with their surgeon, and we will measure the outcomes. Because of this, the study does not change the patient's standard of care; we are simply looking to collect additional data points.

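### Satisfaction, a primary endpoint, is collected only as yes/no, but the 80% power claimed for it comes from a comparison of means and is not shown for this item

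*Combined protocol and SAP*

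**What the plan says.** In section 6 (Study Procedures), question 5 is asked at all six postoperative contacts. The list under Specific data variables to be collected fixes its answer format: "Are you satisfied with the procedure, and would you choose to have it again for a similar problem? Answered with yes or no". The primary endpoints include "The 5 questions asked in the section above, together with the *ADL questionnaire", so this item is primary.

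The Statistical Analysis section assigns categorical data as follows: "We will use Fischer's exact test or a Chi-squared test for differences in categorical variables, depending on the number of events in the different groups". It names Mann-Whitney only for continuous data that are not normally distributed.

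The Power analysis paragraph states: "We have performed a power analysis to find differences between two independent means (normally distributed") "with alpha = 0.05, power = 0.80, and effect size 0.5". It continues: "This would require a total sample size of 102 patients (51 in each group"), with 106 (53 per group) for non-normal data. It ends: "This power analysis is performed for our most important primary outcomes: the 5-question and ADL questionnaires". It gives no sidedness, no expected proportion of yes answers and no calculation for proportions.

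The Background cites earlier studies of ultrasound-guided release as reporting "low rates of catching or locking recurrence rates, high QuickDASH scores and high patient satisfaction", without a figure.

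**The concern.** A power calculation for two means is applied by name to a questionnaire that contains a yes/no item, and the plan tests that item with Fisher or chi-squared. A two-category answer carries less information than a graded one, and least when nearly everyone gives the same answer. The Background suggests that this is likely here.

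Two other yes/no questions have a finer companion measure: the 1–5 activity ratings, and a restart date for work. Satisfaction has none, so grading that is not collected cannot be recovered at analysis.

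If both arms mostly answer yes, a real difference of moderate size would often be missed and could be read as equal satisfaction. Section 3 (Benefits) says the results are meant to support the choice between the two procedures.

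**Working it through.** **Inputs from the plan.** Effect size d = 0.5, alpha 0.05, n = 51 per arm, Fisher or chi-squared for categorical data.

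**Assumptions, not in the plan.** Satisfaction is a latent normal scale; 0.5 is a shift of half an SD on it; 70, 80 or 90% answer yes in the lower arm; no dropout.

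**1. The plan's own figure.** The noncentrality is d√(n/2) = 0.5 × √25.5 = 2.525, with 100 degrees of freedom.
- One-sided: critical t 1.660, power about Φ(2.525 − 1.660) = Φ(0.865) = 80.6%.
- Two-sided: critical t 1.984, power about Φ(0.541) = 70.6%.

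So 51 per arm reproduces only one-sided; two-sided needs 64. For Mann-Whitney, with relative efficiency 3/π, 53 per arm is worth 53 × 0.955 = 50.6 and gives 80.3% one-sided. The plan's figures therefore imply a one-sided test that it never states, and I show both.

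**2. What a half-SD shift means for yes/no.** The other arm's yes rate is p₂ = Φ(Φ⁻¹(p₁) + 0.5):
- 70%: Φ(0.524 + 0.5) = 84.7%
- 80%: Φ(0.842 + 0.5) = 91.0%
- 90%: Φ(1.282 + 0.5) = 96.3%

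**3. Power of the yes/no item.** Full enumeration of both binomials, 51 per arm, chi-squared without continuity correction:

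| Yes rates | Chi-sq, one-sided | Fisher, one-sided | Chi-sq, two-sided | Fisher, two-sided |
|---|---|---|---|---|
| 70 vs 84.7% | 56.4% | 45.9% | 43.3% | 35.0% |
| 80 vs 91.0% | 47.3% | 37.5% | 34.7% | 25.0% |
| 90 vs 96.3% | 37.6% | 19.6% | 22.1% | 10.5% |

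Hand check of the middle row, chi-squared one-sided: the difference is 0.1101 and the pooled rate 0.855. The null SE is √(2 × 0.855 × 0.145/51) = 0.0697, and the alternative SE is √((0.160 + 0.0818)/51) = 0.0689. Power is Φ((0.1101 − 1.645 × 0.0697)/0.0689) = Φ(−0.07), about 47%.

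By the usual two-proportion formula, 80% power would need about 99, 126 and 201 per arm one-sided, or 126, 160 and 256 two-sided.

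**4. Power of a five-level answer.** Same latent shift, three levels below the yes cut and two above it, tie-corrected Mann-Whitney, 40,000 simulations per cell:

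| Satisfied patients choosing the top level | One-sided (70 / 80 / 90% yes) | Two-sided |
|---|---|---|
| One third | 74 / 72 / 69% | 63 / 61 / 58% |
| Half | 73 / 71 / 68% | 61 / 59 / 56% |
| 70% | 69 / 66 / 62% | 57 / 53 / 49% |
| 85% | 64 / 60 / 52% | 52 / 47 / 39% |

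Repeat runs differ by about a point, so the first three rows span about 61–75% one-sided and 49–63% two-sided. With 85% at the top, the one-sided gain over chi-squared is 64 − 56 = 8 points at 70% yes and 52 − 38 = 14 to 15 points at 90% yes. If satisfied patients are not divided at all, the gain all but disappears (37–57% one-sided).

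**The case against.** **The size of the loss depends on unstated inputs.** This stands. The plan gives no yes rate, no sidedness and no effect size for a proportion. A reader might infer that the plan's own effect size by itself takes power from 80% to 20–56%. It does not: that range also needs the latent-normal reading, 70–90% yes in the lower arm and a one-sided test. If 0.5 were read as Cohen's h for two proportions (for example 80 vs 95.5%), one-sided chi-squared power would be about 81% and Fisher 50–73%. The plan ties its 0.5 to two means, so I do not adopt that reading, but nothing in the plan says what a 0.5 effect means for this item.

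**A graded scale may hit a ceiling.** This stands in part. The gain shrinks as more satisfied patients choose the top level. A reader might infer that grading would restore the planned power; no scenario in the table does.

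**A yes/no satisfaction item is a legitimate, readable summary.** This stands. The question also asks whether the patient would choose the procedure again, which is naturally yes/no. A reader might infer that the item should be replaced. That would lose its second half, and the percentage satisfied or very satisfied on a new scale would not equal the present combined yes.

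**The documented fault lies in the power paragraph and needs no new scale.** Correcting that paragraph is indeed the minimum. It would not recover the information that a two-category answer discards.

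**Conclusion.** The concern holds in a limited form. The documents alone establish that a primary endpoint is collected as yes/no, is sent to Fisher or chi-squared, and is said to be covered by a calculation for means; the claimed 80% is not shown for it. How far power falls is conditional. Under the assumptions listed, the yes/no item has about 20–56% one-sided or 11–43% two-sided, against 81% or 71% for means. A five-level answer does better wherever it divides the satisfied patients, by about 8 points or more in the cases tabulated, but stays below 80%. The documents do not support saying that the yes/no format is itself an error, or that the loss has one known size. This is a worthwhile, inexpensive improvement to one primary item; it does not affect the other endpoints.

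**What to change.** - At contacts 2–7, keep question 5 exactly as it is, so that answers already collected stay comparable, and add one five-level satisfaction field (very dissatisfied, dissatisfied, neutral, satisfied, very satisfied).
- In Statistical Analysis, add that ordered categorical answers are compared between arms with Mann-Whitney, since the present text reserves that test for non-normal continuous data.
- In Power analysis, stop claiming 80% for the yes/no item, state whether the test is one- or two-sided, and give the item's power over a stated range of yes rates.

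Cost: one extra REDCap field per contact and a short amendment, with no added visits or patients. Contacts already completed will have no graded answer and can contribute only to the yes/no summary.
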